## 3.2.2 Rituximab and Ruxience

See APPENDIX B for Guidelines for Rituximab and Ruxience Preparation and Administration for infusion times. Briefly, rituximab/Ruxience will be given on day -2 (2 days before day 1) of Cycle 1 and on day 1 of all subsequent cycles. Rituximab/Ruxience are given at 50-400 mg/hr for the 1st dose and may be escalated to 100-400 mg/hr for subsequent doses. Premedication consisting of acetaminophen, famotidine, and diphenhydramine should be considered before each infusion of rituximab/Ruxience (see Section 3.2.3). Since transient hypotension may occur during rituximab/Ruxience infusion, consideration should be given to withholding antihypertensive medications 12 hours before rituximab/Ruxience infusion. If a hypersensitivity (non-IgE-mediated) or an infusion reaction develops, the infusion rate should be reduced to half that rate, i.e. from 100 mg/h to 50 mg/h. Participants who experience a moderate to severe infusion related reaction (fever, chills, or hypotension) should have their infusion interrupted immediately and should receive aggressive symptomatic treatment. The infusion should not be restarted before all the symptoms have disappeared and then the infusion can continue at one-half the previous rate. Dexamethasone 12 mg PO should be given prior to rituximab/Ruxience infusions until moderate-severe infusion reactions are no longer observed.

# 3.2.3 Drug administration scheme

	Cycle 1 only								
Time point	d-2	d1	d2	d3	d4	d5	d6	d7	d8
Treatments									
Rituximab/Ruxience 375 mg/m 	X								
Moxetumomab pasudotox-tdfk 30-40 mcg/kg		X		X		X			
Hydration			•		•		•	•	•
H 2 O (6 L)		X	X	X	X	X	X	X	X
Pre-hydration-5% Dextrose 0.45% NaCl (1 L) 		X		X		X			
Post-hydration-5% Dextrose 0.45% NaCl (1 L) 		X		X		X			
Premedications	'		•		•	•		'	•
Dexamethasone (12 mg)	X								
Acetaminophen (650 mg)	X 	X 		X 		X 			
Diphenhydramine (25-50 mg) 	X								
Famotidine (20-40 mg)	X	X 		X 		X 			
Daily medication									
Aspirin (81 mg) 		X	X	X	X	X	X	X	X

				Cycle	s 2-8			
Time point	d1	d2	d3	d4	d5	d6	d7	d8
Rituximab/Ruxience	X							
Moxetumomab pasudotox-tdfk	X		X		X			
Hydration								
H 2 O (6 L)	X	X	X	X	X	X	X	X
Pre-hydration-5% Dextrose 0.45% NaCl (1 L) 	X		X		X			
Post-hydration-5% Dextrose 0.45% NaCl (1 L) 	X		X		X			
Premedications							•	
Dexamethasone (12 mg)	X 							
Acetaminophen (650 mg)	$X^{1,5}$		X 		X 			
Diphenhydramine (25-50 mg) 	X 							
Famotidine (20 – 40 mg)	X 		X 		X 			
Daily medication	•							
Aspirin (81 mg) 	X	X	X	X	X	X	X	X

Version Date: 04/16/2025

-  To be given 30-90 minutes prior to every moxetumomab pasudotox-tdfk infusion and recommended every 6 hours x 4 after the end of infusion.
-  0.9% Sodium Chloride Injection may be substituted for 5% Dextrose 0.45%NaCl.
- Only if platelet counts  $\geq 100 \times 10^9/L$
-  Administer 0.5-2 hours before rituximab/Ruxience. If participant has previous reaction to rituximab/Ruxience, give 12mg. If participant tolerates rituximab/Ruxience without problems, may hold at discretion of provider.
- Premedications are given prior to rituximab/Ruxience on day 1.
- Famotidine 20 40 mg to be given 30-90 minutes prior to every moxetumomab pasudotox-tdfk infusion and is recommended every 12 hours x 2 after the end of infusion
- May be given prior to moxetumomab pasudotox-tdfk at discretion of PI

#### 3.3 DOSE MODIFICATIONS

Dosing may be delayed up to 4 months for toxicity or logistical reasons, including the inability of the participant to get to the clinic. Treatment cycles need not be delayed for cytopenias but must be delayed for participants in CR presenting grade 3 cytopenia, for grade 3-4 infections and for grade 3-4 neutropenia combined with fever. Any grade >3 infection not resolving within the 4 week delay will be considered DLT.

If participants develop grade 2 CLS, dosing will be delayed until recovery of symptoms; if CLS grade  $\geq$ 3 develops, moxetumomab pasudotox-tdfk will be discontinued.

Any occurrence of DLT as defined in Section 3.1.2 will result in removal from study therapy.

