## 3 STUDY IMPLEMENTATION

## 3.1 STUDY DESIGN

This is a Phase 1 trial, two-arm, non-randomized trial involving the administration of moxetumomab pasudotox-tdfk 30-40 mcg/kg iv and rituximab/Ruxience 375 mg/m² iv, 50-400 mg/hr. The purpose of the rituximab/Ruxience is to decrease the HCL tumor burden, allowing the

Version Date: 04/16/2025

63 kDa immunotoxin to reach all the malignant cells, thereby facilitating tumor eradication, and prevention of neutralization of the immunotoxin by the immune system, through the action of rituximab/Ruxience on normal B-cells. To allow sufficient time for the rituximab/Ruxience to act prior to moxetumomab pasudotox-tdfk, in the first cycle, rituximab/Ruxience will be given on day -2 followed by moxetumomab pasudotox-tdfk on days 1, 3 and 5. Thus on cycle 1 only, moxetumomab pasudotox-tdfk will begin on the 3rd day after rituximab/Ruxience. On subsequent cycles, spaced ~ 4 weeks (as few as 25 days) apart, rituximab/Ruxience will begin on day 1 and moxetumomab pasudotox-tdfk on days 1, 3 and 5. Participants will receive up to 4 cycles past documentation of CR without MRD, up to a maximum of 8 cycles which means, no participant in this trial will receive more than 8 cycles.

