# 3.1.2 Dose Limiting Toxicity

Dose limiting toxicity (DLT) is defined as all treatment related Grade 3 and greater AEs occurring from the initiation of moxetumomab pasudotox-tdfk therapy to within 30 days after the last dose of moxetumomab pasudotox-tdfk treatment. For example, grade >3 cytokine release syndrome, and failure to complete cycle 1 due to toxicity is considered DLT.

Exceptions to DLT include:

- Hematologic toxicity grade 3, or grade 4 resolving within 4 weeks.
- Hematologic toxicity managed with transfusion and/or other support would not constitute DLT.
- Grade 3-4 lymphopenia, leukopenia, or CD4 reductions.
- Grade 3 gastrointestinal toxicity resolving within 72 hours.

- Transaminase and alkaline phosphates elevations grade 3 resolving within 4 weeks.
- Bilirubin elevations associated with Gilbert's syndrome, i.e. total/direct bilirubin ratio ≥4.
- Electrolyte or mineral abnormalities which are grade 3-4, resolving within 4 weeks.
- Grade 3 proteinuria, and fever
- Lipid elevations grade 3 or grade 4 resolving within 4 weeks
- Grade 3 HUS, including HUS-related grade 1-2 creatinine, will not be considered DLT if it resolves within 2 weeks to grade 0-1 creatinine, and is not associated with significant complications including bleeding or need for dialysis or plasmapheresis.
- Allergic reactions to rituximab/Ruxience prevented by desensitization.
- Dosing of both agents must be delayed for any grade 3-4 infection at least possibly related to either drug, and if not resolved despite a 4-week delay will be considered DLT requiring removal from treatment.
- Other isolated grade 3 laboratory abnormalities (not related to CLS or HUS) without clinical signs or symptoms and not associated with clinical sequalae requiring therapeutic intervention.

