## 6.4.2 Complete remission (CR)

All of the following:

- Absolute neutrophil count (ANC)  $\geq 1500/\text{mm}^3$
- Platelets  $\geq 100,000/\text{mm}^3$

Version Date: 04/16/2025

- Hgb  $\geq$  11 g/dL
- Regression of splenomegaly on physical exam or by imaging studies.
- Lymph nodes  $\leq 2$  cm by short axis, unless larger lymph nodes not due to HCL
- Absence of hairy cells on BM aspirate smears and H/E stain of the BM biopsy negative for HCL. If the negative BM is before 4 weeks off of growth factors or transfusions, the CR will begin after the 4 week time point once the normal blood counts are consistent with CR.
- CR with MRD in the BMBx by IHC is defined as CR and a ratio of CD20+ cells to T cells of at least 1, and most of the CD20+ cells consistent with HCL.
- CR with MRD in the peripheral blood is defined as CR and a positive peripheral blood FACS or PCR. Suspicious flow is considered positive per protocol.
- Participants meeting all criteria for CR except minimum levels of ANC, platelets and Hgb will be considered CR if MRD is absent by BMBx IHC and by flow cytometry of blood and bone marrow.

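### Section 3.3 requires a cycle delay for grade 3 cytopenia in CR but, as written, not for isolated grade 4 cytopenia

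*Combined protocol and SAP*

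**What the plan says.** Section 3.3 opens with a permissive rule: "Dosing may be delayed up to 4 months for toxicity or logistical reasons". It then sets the default for low counts, "Treatment cycles need not be delayed for cytopenias", and qualifies it in the same sentence by saying that cycles "must be delayed for participants in CR presenting grade 3 cytopenia, for grade 3-4 infections and for grade 3-4 neutropenia combined with fever". It ends by stating that any DLT as defined in Section 3.1.2 removes the participant from study therapy.

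Section 3.1.2 lists among the exceptions to DLT "Hematologic toxicity grade 3, or grade 4 resolving within 4 weeks", "Hematologic toxicity managed with transfusion and/or other support would not constitute DLT" and "Grade 3-4 lymphopenia, leukopenia, or CD4 reductions".

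Two other provisions decide who is dosed while in CR. Section 3.1 states: "Participants will receive up to 4 cycles past documentation of CR without MRD", with a maximum of 8 cycles. Section 6.4.2 adds a route to CR with low counts: "Participants meeting all criteria for CR except minimum levels of ANC, platelets and Hgb will be considered CR if MRD is absent" by marrow immunohistochemistry and by flow cytometry of blood and marrow.

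**The concern.** The three mandatory triggers sit in one sentence. The infection and febrile neutropenia triggers each span grades 3-4. The trigger for participants in CR stops at grade 3. Taken as printed, a participant in CR with isolated grade 3 cytopenia must wait, while one with isolated grade 4 cytopenia is back under the default and may be dosed on schedule.

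The inversion sits where the protocol intends to be stricter. Cytopenia is a reason for entry (Section 2.1.1.2), which plausibly explains why cycles are not normally held for it. Once a participant is in CR, the leukemia is a less likely cause of low counts, and Section 3.3 singles that group out for a mandatory delay. The stake is the safety of a dosing decision; the definition and analysis of the primary endpoint are unaffected.

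**Working it through.** No figure in the plan is in dispute, so the check is mainly a comparison of provisions, plus a short timing calculation.

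**1. Literal outcome of Section 3.3 for a participant in CR**

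| Event | Provision that applies | Delay |
|---|---|---|
| Isolated grade 3 cytopenia | First trigger | Mandatory |
| Isolated grade 4 cytopenia | None of the three; default | Not required |
| Grade 4 neutropenia with fever | Third trigger | Mandatory |
| Grade 4 infection | Second trigger | Mandatory |

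**2. Is grade 3 used as shorthand for grade 3 or higher?** No. The same sentence writes grade 3-4 twice, the next paragraph writes CLS grade ≥3, and Section 3.1.2 treats hematologic grade 3 and grade 4 separately.

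**3. Does another rule require the delay?**
- The 4-month provision in Section 3.3 permits a delay but does not require one.
- Section 3.2.1 requires counts before every infusion but attaches no hold threshold for cytopenia. By contrast, it does write a mandatory dosing delay for hypercalcemia of grade 2 or higher.
- Under Section 3.1.2, grade 4 hematologic toxicity is not a DLT if it resolves within 4 weeks or is managed with transfusion or other support.
- If it is a DLT, the consequence is removal from therapy. That does not settle whether the next cycle waits while the outcome is still unknown.

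**4. Has the 4-week criterion been reached when the next cycle is due?** Inputs: cycles may be 25 days apart (Section 3.1) and are nominally 28 days (Section 3.4); CBC is scheduled on days 1-5, 8 and 15±3 (Section 3.4).

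Next cycle due: day 1 + 25 = day 26, to day 1 + 28 = day 29. Age of the cytopenia = due day − day first seen.

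| First seen | Age when next cycle is due |
|---|---|
| Day 1 | 26 − 1 = 25 to 29 − 1 = 28 days |
| Day 5 | 26 − 5 = 21 to 29 − 5 = 24 days |
| Day 8 | 26 − 8 = 18 to 29 − 8 = 21 days |
| Day 15 (nominal) | 26 − 15 = 11 to 29 − 15 = 14 days |
| Day 18 (latest in window) | 26 − 18 = 8 to 29 − 18 = 11 days |
| Pre-cycle CBC on the due day | 0 days |

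The 28-day mark is reached only for an event first seen on day 1 of a full 28-day cycle. In the other cases shown, the dosing decision comes before the DLT criterion can be judged.

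**5. Is the situation foreseen?** Yes. Dosing continues for up to 4 cycles after MRD-free CR, and Section 6.4.2 assigns CR to MRD-negative participants whose counts miss the CR minimums. Section 10.2 reports that 7 of the first 9 evaluated participants (7/9 = 78%) reached CR, all MRD-free. These figures show who falls under the CR rule, not how often grade 4 cytopenia occurs in it.

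**The case against.** The strongest reply is that no treating hematologist would hold a participant at grade 3 and dose at grade 4; in a safety rule, grade 3 reads naturally as a threshold. That is probably the intent, and it limits the practical harm. It does not make the text correct, because the protocol writes the full range when it means it.

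A second reply is that a ≥ sign may have been lost in the document text. Some symbols do look doubtful: Section 3.3 prints grade >3 for infections after a rule for grade 3-4 infections, and the Précis prints creatinine < 1.5 where Section 2.1.1.7 has ≤ 1.5. These show at most ≥ reduced to >, not a symbol dropped altogether. The possibility cannot be excluded, but nothing establishes it.

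A third is that the remaining gap is narrow and the event probably uncommon. This largely stands. Fever, grade 3-4 infection, HUS and unsupported treatment-related grade 4 toxicity unresolved at 4 weeks are all handled elsewhere, and the investigator may delay or stop treatment. Ordinary CR requires ANC ≥1500/mm³, platelets ≥100,000/mm³ and Hgb ≥11 g/dL. Section 1.2.1 gives grade 3-4 anemia as 10% and thrombocytopenia or neutropenia as 6.3% with moxetumomab pasudotox alone. Those rates combine grades 3 and 4, disregard attribution, and are not limited to CR.

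A fourth is that a bare change to grade 3-4 could force delays for an expected effect: Section 14.2.2 reports grade 3-4 lymphopenia in 40% of patients treated with rituximab, and Section 3.3 does not define cytopenia. This is right, and it is why the scope must be settled with the correction.

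**Conclusion.** The concern holds. As written, Section 3.3 makes delay mandatory for isolated grade 3 cytopenia in CR and leaves isolated grade 4 to the no-delay default, and no other provision makes that delay mandatory. What is left uncovered is afebrile, uninfected grade 4 cytopenia in a participant in CR that is either supported or less than 4 weeks old, where the investigator chooses to dose.

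The severity is minor. The number of participants affected cannot be estimated from the documents. The conclusion assumes that the printed grade is what the sponsor's document contains; that the intended meaning is grade 3 or higher is an inference for the sponsor to confirm.

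**What to change.** In Section 3.3, change the first trigger so that it covers participants in CR presenting grade 3-4 cytopenia, subject to confirmation by the sponsor's clinicians. In the same edit, state whether lymphopenia, leukopenia and CD4 reductions, which Section 3.1.2 exempts from DLT at grades 3-4, stay outside the delay rule, so that the correction does not force delays for them.

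The cost is one phrase in an amendment plus a short clinical decision on scope. Procedures, data collection and sample size do not change.

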# 3.4 STUDY CALENDAR

						All cycles  (1 cycle=28 days)					
Procedure	Screen/ Baseline	Pre- Cycle 	Cycle 1 Day -2 	Cycle 1 Day -1 	Days 1-5	Day 8	Day 15±3	EOT 	EOT +	F/U 	Restage 
History & PE	X 	X 						X	6m 		X
Vital signs including pulse oximetry 	$X^3$	$X^{20}$			X 	X		X	Λ		Λ
Performance Score	$X^3$	$X^{20}$			Λ	Λ		Λ			
CBC + Diff	$X^3$	X 	X	X	X	X	X	X	X	X 	X
Weight	X	X	71	71	71	X	21	21	21	71	71
Chemistries  , urinalysis	$X^3$	X 	X 	X 	X	X	X	X	X	X 	X
D-Dimer, Fibrinogen, Ferritin, PT/INR, PTT, amylase, lipase, GGT, IgA, IgG, IgM, CRP, haptoglobin	X 	X 	X 	X 	A	X 	A	X	X	A	X
Reticulocyte count, VWF antigen, VWF activity, PAI-1, FDP, p-selectin, thrombomodulin			X	X							
Cytokine panel 13 			X	X							
Immunofixation electrophoresis (IFE) and TBNK	X	X 				X		X	X		X
Flow cytometry	X 	X 						X	X	X	X
EKG	X 	X 						X	X		X
Lipid panel, TSH, FT4, FT3, T4, T3, SPEP	X 							X	X		X
HBcAB, HBsAg, HIV test	X 										
Pregnancy test (females < 50 years)	X 										
24hr urine protein and creatinine	X 					X 					
NIH Advance Directives Form 	X										
CT Neck-pelvis or MRI 	X 	X						X	X		X
MRI C & T-spine 	X 	X						X	X		X

Version Date: 04/16/2025

Echo, PFTs, stress test, abdominal U/S, HLA	X 										
Adverse Events 	X	X						X			
Concomitant Medications 	X 	X						X	X		
Correlative Studies 		(F	lease refer	to Section I	Error! R	eferen	ce source	not fou	nd.)		
BMBx & BMA w/flow and PCR	X 	X 						X	X		X
Blood PCR	X	X						X 	X 		X 
PaxGene RNA & DNA	X 	X						X	X	X	X
Biomarker	X 	X				X		X	X	X	X
ADAs 	X				X 			X	X 		
PBMCs	X 										
Urine (renal proximal tubule cell		X			X 	X					
damage)		$\Lambda$			Λ	$\Lambda$					
PK and PK bioassay 					X 						

- 1. End of treatment visit will occur 28-42 days after 1st dose of last cycle.
- All participants will be offered the opportunity to complete an NIH advance directives form (Section 12.3). This should be done preferably at baseline but can be done at any time during the study. The completion of the form is strongly recommended but not required.
- Within 4 weeks prior to enrollment, could be combined with pre cycle 1. Only anti-moxetumomab pasudotox-tdfk antibodies will be assessed.
- 4. CBC + Diff should be done every 3 months until 2.5y after EOT, then every 6 months.
-  Follow-up time points not requiring restaging are 1, 2 and 3.5 years after EOT, then every 2 years
- 6. Restaging requiring imaging, labs (and bone marrow if CR suspected) is 1.5 and 2.5 years after EOT, then every 2 years.
- Within 6 months of initiation of study therapy provided within 4 weeks after last therapy. Baseline HLA may be done anytime.
- PK and PK bioassay Time points: On days 1 and 5 of cycles 1,2,3,5,7. For cycles 1 and 2: pre, and immediately post, +/- 8 min, then 30+/-10, 60+/-15, 180+/-20,, and 360+/-50 minutes after moxetumomab pasudotox-tdfk end of infusion; On cycles 3, 5, and 7: pre and post infusion, 1-8 min; on cycles 4, 6, and 8 no PK will be drawn. Each ~6cc in K2EDTA tubes.
- 9. CT Neck-Pelvis is done at baseline to identify sites of disease, including spleen, and at EOT and restaging points MRI of these sites may be substituted. In asplenic participants without baseline sites of disease, MRI of the abdomen may be done at restaging time points. The entire neck to pelvis CT need not be repeated if the disease (splenomegaly) was contained within just the abdominal or abdominal-pelvis levels of the CT. Pre-cycle scans will only be performed if participant is being restaged.
- 10. Deviations on post-EOT time points may be +/- 2 months until 2.5 years and +/- 4 months thereafter.
- Chemistries includes sodium, potassium, chloride, bicarbonate, creatinine, glucose, blood urea nitrogen (BUN), albumin, calcium, magnesium, phosphorus, AST (SGPT), ALT (SGOT), total bilirubin, direct bilirubin, lactate dehydrogenase (LDH), total protein, alkaline phosphatase, creatine kinase (CK or CPK), and uric acid. Except on day 15. Day 15 only acute care panel along with CBC with c diff and urine analysis will be required.
- 12. Optional when not performed at NIH
- 13. +/-1 day,

Version Date: 04/16/2025

- To be done at bone marrow time points, to correlate the status of the BMBx with the vertebral BMA signal by MRI. May be cancelled at the discretion of the PI, including if participant unable to get MRI at NIH and not covered by insurance outside NIH.
- 15. This test will be conducted within 3 days prior to enrollment
- 16. Performed within 4 weeks before initiation of study therapy.
- Adverse events and concomitant medications will be monitored continuously in every visit.
- 18. Samples collected during the course of this study will be stored, tracked, and disposed of as specified in investigator's companion protocol, 10C0066, on which all participants will be co-enrolled.
- During the moxetumomab pasudotox-tdfk infusion, vital signs will be obtained every 15 (±10) minutes, then every hour (±30 minutes) for an additional 4 hours during Cycle 1. During subsequent cycles, vital signs will be obtained every 15 (±5) minutes during the moxetumomab pasudotox-tdfk infusion, then every hour (±30 minutes) for an additional 2 hours. Vital signs will also be obtained on Day 8 ± 1 day for the first 3 dosing cycles.
-  May be done up to 3 days prior to day 1 of cycle.
- Must be done on day 1 of cycle 1 prior to treatment.
- 22. Cycle interval may be shortened to 25-27 days due to logistical reasons.
-  Pre-cycle tests may be done 0 to 2 days before and maybe combined with either baseline for cycle 1 or day 1 or both.
- 24. During rituximab/Ruxience infusion on cycle 1 day -2 vital signs will be obtained with every dose change and as needed.
- 25. Must be completed on day 8 but may be cancelled at PI discretion.
- 26. Pre-cycle and pretreatment on days 3, 5, and 8.
- 27. Pre-cycle bone marrow and scans to be done at the discretion of the PI based on the participants HR status.
- 28. Sampling pre-dose before cycles 1,2,3,5, and 7.
- 29. Sampling at 3 and 6 months after the end of treatment evaluation.
- 30. Sampling in case HUS or CLS are observed.
- 31. Cycle 1 IFE to be done pre cycle may be combined with baseline labs +/- 1-4 days and again pre moxetumomab pasudotox-tdfk on Cycle 1 day1.
- 32. Screening labs can be combined with pre cycle 1 labs if done within 5 days of day -2 with the exception of the labs listed as day -2 labs
- Pre-rituximab/Ruxience and 6-8 hours post-rituximab/Ruxience. It includes: Tumor Necrosis Factor-alpha, interleukin 2, interleukin 2 receptor soluble, interleukin 12, interleukin 12, interleukin 4, interleukin 5, interleukin 10, interleukin 13, interleukin 17, interleukin 1 beta, interleukin 6, and interleukin 8.
- 34. Day -2 pre Rituxan and 6-8 hours after the start of Rituxan.
- 35. AM of day -1
- 36. LDH only
- 37. D-dimer and haptoglobin only
- 38. Optional

Version Date: 04/16/2025

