#### 3.2 DRUG ADMINISTRATION

## 3.2.1 Moxetumomab pasudotox-tdfk

Moxetumomab pasudotox-tdfk is administered at 30-40 mcg/kg intravenous (IV) over 30 min using early call back/reverse flow method (intended dose level 1). Moxetumomab pasudotox-tdfk is given on days 1, 3, and 5 of each cycle. When given on the same day as a rituximab/Ruxience infusion, the rituximab/Ruxience will be given first followed by Moxetumomab pasudotox-tdfk. Participants will receive up to 4 cycles past documentation of CR without MRD, maximum 8. To prevent renal toxicity and hypovolemia, participants will be encouraged to drink water gradually, approximately 1 cup/hour or 6L/day, and to avoid going >3 hours without drinking from days 1 to 8. To prevent rituximab/Ruxience toxicity, participants will receive prophylactic dexamethasone as indicated in Section 3.2.3, before the 1st dose of rituximab/Ruxience, and before subsequent doses until rituximab/Ruxience infusion reactions are not seen. Diphenhydramine, famotidine, and acetaminophen may be used as needed. Dexamethasone 4 mg orally (maximum 2 doses/24 hours) will be given to treat nausea or fever associated with moxetumomab pasudotox-tdfk, which otherwise might prevent adequate water intake.

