## 3.6 CRITERIA FOR REMOVAL FROM PROTOCOL THERAPY AND OFF STUDY CRITERIA

Prior to removal from the study, effort must be made to have all participants complete a safety visit approximately 28-42 days following the last dose of study therapy.

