## 6 DATA COLLECTION AND EVALUATION

#### 6.1 DATA COLLECTION

The PI will be responsible for overseeing entry of data a 21 CFR Part 11-compliant data capture system provided by the NCI CCR and ensuring data accuracy, consistency and timeliness. The principal investigator, associate investigators/research nurses and/or a contracted data manager will assist with the data management efforts. Primary and final analyzed data will have identifiers so that research data can be attributed to an individual human subject participant.

All adverse events, including clinically significant abnormal findings on laboratory evaluations, regardless of severity, will be followed until return to baseline or stabilization of event.

Document AEs from the first study intervention, Study Day 1, through the end of treatment. After 30 days, only adverse events which are serious and related to the study intervention need to be recorded.

An abnormal laboratory value will be recorded in the database as an AE **only** if the laboratory abnormality is characterized by any of the following:

- Results in discontinuation from the study
- Is associated with clinical signs or symptoms
- Requires treatment or any other therapeutic intervention
- Is associated with death or another serious adverse event, including hospitalization.
- Is judged by the Investigator to be of significant clinical impact
- If any abnormal laboratory result is considered clinically significant, the investigator will provide details about the action taken with respect to the test drug and about the participant's outcome.

**End of study procedures:** Data will be stored according to HHS, FDA regulations, and NIH Intramural Records Retention Schedule as applicable.

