# 8.4.3.2 Reporting of Adverse events (AEs)

AEs for new primary malignant tumors reported during a study should generally be assessed as serious AEs. If no other seriousness criteria apply, the 'important medical event' criterion should be used. In certain situations, however, medical judgement on an individual event basis should be applied to clarify that the primary malignant tumor event should be assessed and reported as a non-serious AE. For example, if the tumor is included as medical history and progression occurs during the study, but the progression does not change treatment and/or prognosis of the malignant tumor, the AE may not fulfil the attributes for being assessed as serious, although reporting of the progression of the malignant tumor as an AE is valid and should occur. Also, some types of malignant tumors, which do not spread remotely after a routine treatment that does not require hospitalization, may be assessed as non-serious; examples include Stage I basal cell carcinoma and Stage IA1 cervical cancer removed via cone biopsy.

Non-serious adverse events and SAEs will be collected from the time consent is given, throughout the treatment period and up to and including the 30-day follow-up period. After withdrawal from treatment, subjects must be followed up for all existing and new AEs for 30 calendar days after the last dose of trial drug and/or until event resolution. All new AEs occurring during that period must be recorded (if SAEs, then they must be reported as indicated in Sections 8.3 and 8.4.1). All study-related toxicities/ SAEs must be followed until resolution, unless in the Investigator's opinion, the condition is unlikely to resolve due to the patient's underlying disease.

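### The end-of-treatment visit may fall up to 6 days before the 30-day DLT window closes, and no later laboratory draw covers the remaining days

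*Combined protocol and SAP*

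**What the plan says.** **The DLT window.** Section 3.1.2 counts qualifying events from the start of moxetumomab "to within 30 days after the last dose of moxetumomab pasudotox-tdfk treatment". Section 3.2.1 gives the dosing days: "Moxetumomab pasudotox-tdfk is given on days 1, 3, and 5 of each cycle". Section 10.4.2 defines success on the primary safety endpoint as 10 treated participants with no more than 2 DLTs.

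**The visit, with two anchors.** Section 3.4, footnote 1: "End of treatment visit will occur 28-42 days after 1st dose of last cycle". Section 3.6 asks that effort be made, before removal from the study, to have participants "complete a safety visit approximately 28-42 days following the last dose of study therapy". The interval is the same, but one is counted from the first dose of the last cycle and the other from the last dose. Section 3.6.1 sends participants who are off treatment but still on study back to the Section 3.4 schedule.

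**The adverse event recording period, also stated two ways.** Section 6.1: "Document AEs from the first study intervention, Study Day 1, through the end of treatment". Its next sentence limits recording after 30 days to serious related events, without saying 30 days from what. Section 8.4.3.2 is definite: collection runs "throughout the treatment period and up to and including the 30-day follow-up period", and "subjects must be followed up for all existing and new AEs for 30 calendar days after the last dose of trial drug". Section 8.2 refers the reader to Section 6.1, not to Section 8.4.3.2, for the recording timeframe.

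**Scheduled tests after the visit.** The calendar and its footnotes give a CBC every 3 months and the next full chemistry at 6 months after the end-of-treatment visit.

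**The concern.** The primary endpoint is a small count of DLTs, and the window for that count is fixed by the last dose. The last scheduled full laboratory assessment of the treatment period is fixed by the first dose of the cycle. The two clocks differ by four days in a completed cycle, and the visit may open at 28 days where the window needs 30. The visit can therefore take place while the window is still open.

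This matters most for events found by laboratory test. Section 3.2.1 monitors for HUS through hemoglobin, platelets and serum creatinine. Several exceptions in Section 3.1.2 also turn on whether an abnormality resolved within 2 or 4 weeks, which needs a later measurement. Participants with the same clinical course could have laboratory observation of different lengths depending on the day they were booked.

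**Working it through.** **The plan's own figure.** Section 10.2 gives an upper one-sided 90% bound of 45.0% on 2 DLTs in 10. The exact (Clopper-Pearson) bound is the 0.90 quantile of Beta(3, 8) = 0.4496, which agrees. The timing issue does not alter this figure; it concerns whether the count entering it is complete.

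**Timing after a completed cycle.** Inputs: dosing on days 1, 3 and 5 (Section 3.2.1); DLT window to 30 days after the last dose (Section 3.1.2); visit 28 to 42 days after the first dose (Section 3.4, footnote 1).

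- Last dose = first dose + 4 days.
- Window closes at 4 + 30 = 34 days after the first dose.
- Permitted visit days: 28 to 42, so 42 − 28 + 1 = 15 days.
- Visit days before the close: 28 to 33, so 6 of 15.
- Earliest visit: 28 − 4 = 24 days after the last dose, 6 days short of 30.
- Latest visit: 42 − 4 = 38 days after the last dose, no shortfall.

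**Variants.**

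| Reading | Earliest visit, days after last moxetumomab dose | Shortfall against 30 days |
|---|---|---|
| Footnote 1, last dose on day 5 | 24 | 6 |
| Footnote 1, dosing stopped after day 3 | 26 | 4 |
| Footnote 1, dosing stopped after day 1 | 28 | 2 |
| Footnote 1, cycle 1 is last, first dose read as the day −2 antibody | 21 or 22 | 9 or 8 |
| Section 3.6, counted from last dose | 28 | 2 |

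The fourth row depends on reading the antibody infusion as the first dose; the two values reflect whether day 0 is counted. No row guarantees a visit at or after day 30.

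**Share of the window.** Six days is 6/30 = 20% of the period after the last dose. The DLT window, however, starts with the first moxetumomab dose. For one cycle the share is 6/34 = 17.6%. For eight 28-day cycles the window is 7 × 28 + 34 = 230 days, and the share is 6/230 = 2.6%.

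**Direction of the effect.** The documents give no rate of DLTs first arising late in the last cycle, so the following is illustration only. Assume a true DLT probability p, with a fraction m of DLTs missed. The chance of passing is P(X ≤ 2), with X binomial(10, p(1 − m)).

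| Assumed p | m = 0 | m = 5% | m = 20% |
|---|---|---|---|
| 20% | 0.678 | 0.708 | 0.794 |
| 30% | 0.383 | 0.424 | 0.556 |
| 40% | 0.167 | 0.202 | 0.331 |

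Missed events can only make the rule easier to pass. Here m is a fraction of events and must not be read off the fraction of days.

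**The case against.** A reader might infer that the end-of-treatment visit closes DLT scoring, so that any later event inside the window would be counted as no DLT. The documents do not say this. Section 3.1.2 defines a DLT by when the event occurs. Section 8.4.3.2 requires all new adverse events in the 30 days after the last dose to be recorded, and the second sentence of Section 6.1 is most naturally read the same way. Calendar footnote 17 asks for continuous adverse event monitoring at every visit. A symptomatic event should therefore be captured whenever the visit took place.

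A reader might also take 20% as the unobserved share of the DLT window. That figure is the worst case for the period after the last dose only.

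The pathway to harm is narrow. Section 3.1.2 exempts, subject to conditions, isolated grade 3 laboratory abnormalities without clinical signs (unless related to HUS or CLS), grade 3 hematologic toxicity, many liver-enzyme and electrolyte abnormalities that resolve within 4 weeks, and grade 3 HUS that resolves within 2 weeks without significant complications. Section 3.1.3.1 already makes entry of the 4th and 7th evaluable participants wait at least 30 days after the last dose of cycle 2 (or of cycle 1), so those steps do not depend on this visit. Section 3.6 may also describe a separate visit, which would reduce the shortfall to at most 2 days.

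These points limit the concern but do not remove it. A duty to record cannot reveal an abnormality that nobody has measured. The Section 3.6 visit is approximate, requires only effort, and can itself fall on day 28. Section 8.2 also directs staff to the less definite of the two recording rules.

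**Conclusion.** The conflict between footnote 1 and Section 3.6 is real, and under either anchor the visit can precede the close of the DLT window: by up to 6 days under footnote 1 after a completed cycle, and by up to 2 days under Section 3.6. The consequence is limited to a silent, laboratory-detected DLT, mainly HUS- or CLS-related or grade 4, arising late in the last cycle after an early visit. Such an event could go undetected.

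The effect on the rule of no more than 2 in 10 cannot be quantified from the documents. One might infer that a single missed event would overturn the safety conclusion; the reported data do not point that way. Section 3.1.4 records 9 participants at 40 mcg/kg without DLT as of 24 September 2021. If that status held through their treatment, a third DLT among the ten would need at least two missed events in those nine plus one in the tenth (3 − 1 = 2). Nor do the documents show that any event was missed. The point is worth correcting because DLT presence or absence is also the focus of the safety analysis (Section 10.4.4), and the correction is cheap.

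**What to change.** 1. Use one visit definition in Section 3.4, footnote 1, and Section 3.6, counted from the last moxetumomab dose and opening no earlier than day 30 after it, for example 30 to 42 days.
2. In Section 6.1, state that all adverse events are recorded through 30 days after the last dose, in line with Sections 3.1.2 and 8.4.3.2, and name that dose as the anchor for the sentence on events after 30 days.
3. State that a participant's DLT status is closed only at or after this visit.
4. For participants already seen earlier, review existing records through day 30 where available. Report how many had the end-of-treatment visit before day 30 after the last dose. Laboratory results for those days may not exist, and the report should say so where that is the case.

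The cost is a few sentences in an amendment and a limited record review. After a completed cycle the earliest permitted visit moves from 28 to 34 days after the first dose, so some visits take place up to about a week later. No new procedure is needed.
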